7.2.2 Reporting of Pregnancy and Lactation to the Sponsor and to Merck

Although pregnancy and lactation are not considered adverse events, it is the responsibility of investigators or their designees to report any pregnancy of a male subject's female partner that occurs during the trial or within 120 days of completing the trial completing the trial, or 30 days following cessation of treatment if the subject initiates new anticancer therapy, whichever is earlier. All female partners of male subjects who become pregnant must be followed to the completion/termination of the pregnancy. Pregnancy outcomes of spontaneous abortion, missed abortion, benign hydatidiform mole, blighted ovum, fetal death, intrauterine death, miscarriage and stillbirth must be reported as serious events (Important Medical Events). If the pregnancy continues to term, the outcome (health of infant) must also be reported.

From the time these events become known to the study team, they must be reported within 24 hours to the Sponsor and within 2 working days to Merck Global Safety. (Attn: Worldwide Product Safety; [contact])

7.2.3 Immediate Reporting of Adverse Events to the Sponsor and to Merck

7.2.3.1 Serious Adverse Events

A serious adverse event is any adverse event occurring at any dose or during any use of Merck's product that:

- Results in death;
- Is life threatening;
- Results in persistent or significant disability/incapacity;
- Results in or prolongs an existing inpatient hospitalization;
- Is a congenital anomaly/birth defect;
- Is a new cancer (that is not a condition of the study);
- Is associated with an overdose;
- Is any other important medical event

Refer to Table 9 for additional details regarding each of the above criteria.

Progression of the cancer under study is not considered an adverse event unless it results in hospitalization or death.

Any serious adverse event, or follow up to a serious adverse event, including death due to any cause other than progression of the cancer under study that occurs to any subject from the time the consent is signed through 90 days following cessation of treatment, or the initiation of new anti-cancer therapy, whichever is earlier, whether or not related to Merck product, must be reported within 24 hours to the Sponsor and within 2 working days to Merck Global Safety. The clock begins at the time the study team learns of the event.

Non-serious Events of Clinical Interest will be forwarded to the Sponsor (OHSU) and to Merck Global Safety and will be handled in the same manner as SAEs.

Additionally, any serious adverse event, considered by an investigator who is a qualified physician to be related to Merck product that is brought to the attention of the investigator at any time outside of the time period specified in the previous paragraph also must be reported immediately to the Sponsor and to Merck.

SAE reports and any other relevant safety information are to be forwarded to the Merck Global Safety [contact]

A copy of all 15 Day Reports and Annual Progress Reports is submitted as required by FDA, European Union (EU), Pharmaceutical and Medical Devices agency (PMDA) or other local regulators. Investigators will cross reference this submission according to local regulations to the Merck Investigational Compound Number (IND, CSA, etc.) at the time of submission. Additionally investigators will submit a copy of these reports to Merck & Co., Inc. (Attn: Worldwide Product Safety; [contact]) at the time of submission to FDA.

All subjects with serious adverse events must be followed up for outcome.

7.2.3.2 Events of Clinical Interest

Selected non-serious and serious adverse events are also known as Events of Clinical Interest (ECI) and must be recorded as such on the Adverse Event case report forms/worksheets and reported within 24 hours to the Sponsor and within 2 working days to Merck Global Safety. (Attn: Worldwide Product Safety; [contact])

Events of clinical interest for this trial include:

1. an overdose of Merck product, as defined in Section 7.2.1 - Definition of an Overdose for This Protocol and Reporting of Overdose to the Sponsor, that is not associated with clinical symptoms or abnormal laboratory results.
2. an elevated AST or ALT lab value that is greater than or equal to 3X the upper limit of normal and an elevated total bilirubin lab value that is greater than or equal to 2X the upper limit of normal and, at the same time, an alkaline phosphatase lab value that is less than 2X the upper limit of normal, as determined by way of protocol-specified laboratory testing or unscheduled laboratory testing.*

***Note:** These criteria are based upon available regulatory guidance documents. The purpose of the criteria is to specify a threshold of abnormal hepatic tests that may require an additional evaluation for an underlying etiology. The trial site guidance for assessment and follow up of these criteria can be found in the Investigator Trial File Binder (or equivalent).

3. In the event a subject develops any of the following AEs, a detailed narrative of the event should be reported as an ECI to the Sponsor within 24 hours and to Merck Global Safety within 2 working days of the event:
 - a. Grade ≥ 3 diarrhea
 - b. Grade ≥ 2 colitis
 - c. Grade ≥ 2 pneumonitis
 - d. Grade ≥ 3 hypo- or hyperthyroidism

A separate guidance document has been provided entitled “event of Clinical Interest and Immune-Related Adverse Event Guidance Document.” This document provides guidance regarding identification, evaluation and management of ECIs and irAEs. Additional ECIs are identified in this guidance document and also need to be reported to the Sponsor within 24 hours and to Merck Global Safety within 2 working days of the event.

Subjects should be assessed for possible ECIs prior to each dose. Lab results should be evaluated and subjects should be asked for signs and symptoms suggestive of an immune-related event. Subjects who develop an ECI thought to be immune-related should have additional testing to rule out other etiologic causes. If lab results or symptoms indicate a possible immune-related ECI, then additional testing should be performed to rule out other etiologic causes. If no other cause is found, then it is assumed to be immune-related.

ECIs that occur in any subject from the date of first dose through 90 days following cessation of treatment, or the initiation of a new anticancer therapy, whichever is earlier, whether or not related to the Merck's product, must be reported within 24 hours to the Sponsor and to Merck Global Safety within 2 working days.

7.2.3.3 Responsibility of Participating Sites

Participating sites are responsible for reporting all SAEs to their local IRB per local guideline.

Participating sites are responsible for reporting all SAEs and Events of Clinical Interest to OHSU via fax or email within 24 hours of becoming aware of the event. Please see section 7.2.3.1 and 7.2.3.2.

Responsibility of OHSU

The OHSU research staff is responsible for submitting all SAEs/UPs to the OHSU IRB.

The OHSU research staff is responsible for submitting all SAEs and Events of Clinical Interest to Merck Global Safety.

The OHSU PI is responsible for informing all participating sites about all SAEs.

7.2.4 Evaluating Adverse Events

An investigator who is a qualified physician will evaluate all adverse events according to the NCI Common Terminology for Adverse Events (CTCAE), version 4.0. Any adverse event which changes CTCAE grade over the course of a given episode will have each change of grade recorded on the adverse event case report forms/worksheets.

All adverse events regardless of CTCAE grade must also be evaluated for seriousness.

Table 9 Evaluating Adverse Events

An investigator who is a qualified physician, will evaluate all adverse events as to:

V4.0 CTCAE Grading	Grade 1	Mild; asymptomatic or mild symptoms; clinical or diagnostic observations only; intervention not indicated.
	Grade 2	Moderate; minimal, local or noninvasive intervention indicated; limiting age-appropriate instrumental ADL.
	Grade 3	Severe or medically significant but not immediately life-threatening; hospitalization or prolongation or hospitalization indicated; disabling; limiting self-care ADL.
	Grade 4	Life threatening consequences; urgent intervention indicated.
	Grade 5	Death related to AE
Seriousness	A serious adverse event is any adverse event occurring at any dose or during any use of Merck product that:	
	†Results in death; or	
	†Is life threatening; or places the subject, in the view of the investigator, at immediate risk of death from the event as it occurred (Note: This does not include an adverse event that, had it occurred in a more severe form, might have caused death.); or	
	†Results in a persistent or significant disability/incapacity (substantial disruption of one's ability to conduct normal life functions); or	
	†Results in or prolongs an existing inpatient hospitalization (hospitalization is defined as an inpatient admission, regardless of length of stay, even if the hospitalization is a precautionary measure for continued observation. (Note: Hospitalization [including hospitalization for an elective procedure] for a preexisting condition which has not worsened does not constitute a serious adverse event.); or	
	†Is a congenital anomaly/birth defect (in offspring of subject taking the product regardless of time to diagnosis); or	
	Is a new cancer; (that is not a condition of the study) or	
	Is an overdose (whether accidental or intentional). Any adverse event associated with an overdose is considered a serious adverse event. An overdose that is not associated with an adverse event is considered a non-serious event of clinical interest and must be reported within 24 hours.	
	Other important medical events that may not result in death, not be life threatening, or not require hospitalization may be considered a serious adverse event when, based upon appropriate medical judgment, the event may jeopardize the subject and may require medical or surgical intervention to prevent one of the outcomes listed previously (designated above by a †).	
Duration	Record the start and stop dates of the adverse event. If less than 1 day, indicate the appropriate length of time and units	
Action taken	Did the adverse event cause the Merck product to be discontinued?	
Relationship to test drug	Did the Merck product cause the adverse event? The determination of the likelihood that the Merck product caused the adverse event will be provided by an investigator who is a qualified physician. The investigator's signed/dated initials on the source document or worksheet that supports the causality noted on the AE form, ensures that a medically qualified assessment of causality was done. This initialed document must be retained for the required regulatory time frame. The criteria below are intended as reference guidelines to assist the investigator in assessing the likelihood of a relationship between the test drug and the adverse event based upon the available information. The following components are to be used to assess the relationship between the Merck product and the AE; the greater the correlation with the components and their respective elements (in number and/or intensity), the more likely the Merck product caused the adverse event (AE):	
	Exposure	Is there evidence that the subject was actually exposed to the Merck product such as: reliable history, acceptable compliance assessment (pill count, diary, etc.), expected pharmacologic effect, or measurement of drug/metabolite in bodily specimen?
	Time Course	Did the AE follow in a reasonable temporal sequence from administration of the Merck product? Is the time of onset of the AE compatible with a drug-induced effect (applies to trials with investigational medicinal product)?
	Likely Cause	Is the AE not reasonably explained by another etiology such as underlying disease, other drug(s)/vaccine(s), or other host or environmental factors

The following components are to be used to assess the relationship between the test drug and the AE: (continued)			
Relationship to Merck product (continued)	Dechallenge	
Was the Merck product discontinued or dose/exposure/frequency reduced? If yes, did the AE resolve or improve? If yes, this is a positive dechallenge. If no, this is a negative dechallenge. (Note: This criterion is not applicable if: (1) the AE resulted in death or permanent disability; (2) the AE resolved/improved despite continuation of the Merck product; or (3) the trial is a single-dose drug trial); or (4) Merck product(s) is/are only used one time.)
	
	Rechallenge	
Was the subject re-exposed to the Merck product in this study? If yes, did the AE recur or worsen? If yes, this is a positive rechallenge. If no, this is a negative rechallenge. (Note: This criterion is not applicable if: (1) the initial AE resulted in death or permanent disability, or (2) the trial is a single-dose drug trial); or (3) Merck product(s) is/are used only one time).
 
NOTE: IF A RECHALLENGE IS PLANNED FOR AN ADVERSE EVENT WHICH WAS SERIOUS AND WHICH MAY HAVE BEEN CAUSED BY THE MERCK PRODUCT, OR IF REEXPOSURE TO THE MERCK PRODUCT POSES ADDITIONAL POTENTIAL SIGNIFICANT RISK TO THE SUBJECT, THEN THE RECHALLENGE MUST BE APPROVED IN ADVANCE BY THE U.S. CLINICAL MONITOR AS PER DOSE MODIFICATION GUIDELINES IN THE PROTOCOL.
	
	Consistency with Trial Treatment Profile	Is the clinical/pathological presentation of the AE consistent with previous knowledge regarding the Merck product or drug class pharmacology or toxicology?	
The assessment of relationship will be reported on the case report forms /worksheets by an investigator who is a qualified physician according to his/her best clinical judgment, including consideration of the above elements.			
Record one of the following		Use the following scale of criteria as guidance (not all criteria must be present to be indicative of a Merck product relationship).	
Yes, there is a reasonable possibility of Merck product relationship.		There is evidence of exposure to the Merck product. The temporal sequence of the AE onset relative to the administration of the Merck product is reasonable. The AE is more likely explained by the Merck product than by another cause.	
No, there is not a reasonable possibility Merck product relationship		Subject did not receive the Merck product OR temporal sequence of the AE onset relative to administration of the Merck product is not reasonable OR there is another obvious cause of the AE. (Also entered for a subject with overdose without an associated AE.)	

7.2.5 Responsibility for Reporting Adverse Events

All Adverse Events will be reported to regulatory authorities, IRB/IECs and investigators in accordance with all applicable global laws and regulations.

8.0 STATISTICAL ANALYSIS PLAN

This is a single-arm phase II clinical trial to examine the efficacy of pembrolizumab in men with mCRPC who initially responded to single-agent enzalutamide but who are currently experiencing a PSA progression.

8.1 Primary and Secondary Endpoints

Primary endpoint: PSA response, defined by a PSA decrease of at least 50% confirmed by a second measurement at least 3 weeks later.

Secondary endpoints:

- % change in PSA
- Immunological parameters, including leukocytes, lymphocytes (CD8+, CD4+, and B cells), and macrophages in prostate tissue at diagnosis (if original biopsy is available) and pre-treatment.
- Immunohistochemistry for PD-1, PD-L1 and PD-L2 in prostate tissue at diagnosis (if original biopsy is available) and pre-treatment
- Circulating tumor cells (CTCs) (binary variable)
- Changes in T cell numbers, activation, and phenotype as measured in PBMC at diagnosis and throughout therapy, including T effector/memory panel (CD45, CD3, CD8, CCR7, CD45RA, CD45RO, CD69, CD44, CD62L), T regulatory panel (CD45, CD3, CD4, FoxP3, CD25, CD127, CD69, CD44), T help panel (CD45, CD3, CD4, CD45RA, CD45RO, CD69, CD44, CD62L), and cytokine propensity of the above T cell subsets (IFN- γ , IL-2, IL-4, IL-12, IL-13, IL-10, IL-18, TNF- α , TGF- β , IL-17)
- Systemic inflammatory markers: Serum IL-8, IL-6, IL-1, TNF and TGF-beta
- Objective disease response by radiographs
- Overall survival
- PSA progression free survival where the definition of progression will be PSA progression per Prostate Cancer Working Group 2 criteria. If there is a decline from baseline, progression is an increase in PSA that is 25% and 2 ng/ml above the nadir, which is confirmed by a second value 3 or more weeks later (i.e., a confirmed rising trend)

- DNA mutations.

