2.2 Trial Diagram

3.0 OBJECTIVES & HYPOTHESES

3.1 Primary Objectives & Hypotheses

Objectives: Measure the anti-cancer activity of pembrolizumab in men with metastatic, castration resistant prostate cancer. A response to treatment will be defined by a PSA decrease of at least 50%. Examine the safety of the combination of pembrolizumab with enzalutamide by looking at adverse events by the CTCAE v.4.

Hypothesis: Immunological therapy with pembrolizumab combined with a second generation receptor antagonist will be safe and lead to PSA responses in men with mCRPC beginning to progress on enzalutamide.

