5.5 Concomitant Medications/Vaccinations (allowed & prohibited)

Medications or vaccinations specifically prohibited in the exclusion criteria are not allowed during the ongoing trial. If there is a clinical indication for one of these or other medications or vaccinations specifically prohibited during the trial, discontinuation from trial therapy or vaccination may be required. The investigator should discuss any questions regarding this with [name]. The final decision on any supportive therapy or vaccination rests with the investigator and/or the subject's primary physician. However, the decision to continue the subject on trial therapy or vaccination schedule requires the mutual agreement of the Investigator and the subject.

External beam radiation therapy is permitted on this study. Its use should be disclosed and described (dose, number of areas, number of treatments, treatment dates and response) as a Concomitant Therapy in clinical report forms. There are no data regarding the simultaneous use of radiation and pembrolizumab. Therefore, if radiation is needed, the pembrolizumab should be held one week prior to radiation and for 2 weeks after radiation therapy.

Subjects eligible for this study are progressing on enzalutamide and must continue the enzalutamide while on this study. However, enzalutamide may be held for adverse events thought to be related to enzalutamide. If a subject is off of enzalutamide for longer than 30 consecutive days, either directly prior to starting the study or after enrollment, the principal investigator needs to be alerted.

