7.1.2.12 Disease Response Criteria

PSA decrease of at least 50%.

Radiographic Response will be determined using RECIST 1.1.(33)

[See Section 12.3.](#)

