8.2 Statistical Analysis Plan

Descriptive statistical analysis will be conducted for all primary and secondary endpoints, for all patients, and for subgroups (abiraterone versus no prior abiraterone and sipuleucel-T versus no prior sipuleucel-T). The proportion estimate will be reported with 95% confidence interval, and the continuous variables will be summarized using nmissing, mean, std, median, min, and max. Safety and adverse events will be presented in a tabular form.

One-sample binomial test will be used to assess whether the proportion of PSA response (PSA decrease of at least 50%) is significantly greater than 0.05. Univariable logistic regression analysis will be conducted to assess the association between immunological parameters and PSA response responses. Scale in logit will be assessed for all continuous parameters that are identified to be significantly associated with PSA response. Our hypothesis is that Microsatellite instability and PD-L1 expression together with other immunological parameters are potential predictors for PSA response. As the incidence of MSI and the presence of PD-L1 expression are relatively small (under 10% for MSI), we propose to enroll 30 additional subjects to this study to help find 1) whether MSI and PD-L1 expression are likely predictors for PSA response and 2) whether any other immunological parameters independently or jointly predicts the PSA response. Multivariable logistic regression model will be fitted to identify the potential predictors. Stepwise variable selection will be used to find the final model. Random forest will also be used as a parallel method for building the predictive model. The area under the Receiver Operating Characteristic (ROC) curve will be computed for the discrimination ability of the predictive model. 10-fold cross validation will be performed to assess the validation of the proposed model. Due to the limited sample size, we will not have a separate testing set to validate the predictive model. Therefore, all findings are exploratory and need to be validated. Kaplan-Meier curve will be plotted to illustrate the PSA progression free survival for all, and for subgroups (abiraterone versus no prior abiraterone and sipuleucel-T versus no prior sipuleucel-T).

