8.3 Sample Size Computation

Patients with PSA progression on treatment are extremely unlikely to have a PSA response without a change in therapy. If 25% of subjects treated with pembrolizumab upon progression with enzalutamide have a PSA response, this therapy would be worthy of further study. Using a null hypothesis of 5% and alternate hypothesis of 25%, 25 evaluable patients are needed with 90% power and a one-sided alpha of 0.05. To account for potential drop-out, we will enroll 28 subjects.

We propose to add 30 additional subjects to this study (for a total of 58) to better evaluate the association between PSA responses and candidate risk factors (MSI and PD-L1 expression with other immunological parameters), and to build a prognostic model. The proposed sample size will achieve 80% power to detect AUC of 0.85 against AUC of 0.6 using two-sided z test at 5% significance level. We understand that it is not guaranteed that a predictive model with good predictive ability can be constructed, because both MSI and PD-L1 expressions are relatively rare. However, the collected data and analysis will be clinically valuable to help us determine whether a future larger study is worthy. . In the initial study, we did biopsies on any subject that had a

metastatic lesion that could be biopsied, but subjects were not required to have a lesion that could be biopsied. We are doing biopsies on all 30 additional patients along with the tests we did on earlier participants.

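### The primary test in section 8.2 omits the confirmation that section 8.1 requires, and with no last eligible PSA a fall after permitted external beam radiation can count as a response against the 5% null

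*Combined protocol and SAP*

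**What the plan says.** **Definition of response.** Section 8.1 gives the primary endpoint as "PSA response, defined by a PSA decrease of at least 50% confirmed by a second measurement at least 3 weeks later". Section 8.2 says the one-sample binomial test will assess "whether the proportion of PSA response (PSA decrease of at least 50%) is significantly greater than 0.05". Section 3.1 says "A response to treatment will be defined by a PSA decrease of at least 50" per cent, and section 7.1.2.12 says only "PSA decrease of at least 50" per cent. Confirmation therefore appears in one of the four places.

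**Reference and window.** None of the four names the value from which the fall is measured. The flow chart (section 6.1) draws PSA at screening (day -28 to -1) and again at Cycle 1. It then draws PSA at each later cycle, after the first course, every 6 weeks in Monitoring, through retreatment, at discontinuation and at safety follow-up. Section 7.1.5.4 allows retreatment without limit. No last eligible PSA is stated.

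**Radiation.** Section 5.5 states that "External beam radiation therapy is permitted on this study". It requires dates and dose to be recorded, and holds pembrolizumab around the radiation rather than ending participation. Section 8 has no rule for PSA values drawn afterwards.

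**The null.** Section 8.3 sets 5% against 25% and says "25 evaluable patients are needed with 90% power and a one-sided alpha of 0.05". It opens with "Patients with PSA progression on treatment are extremely unlikely to have a PSA response without a change in therapy". Enrolment was 28 and is now 58.

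**The concern.** With no control arm, only the endpoint definition separates a PSA fall on the tested regimen from a fall that follows something else. As written, a man irradiated in Monitoring whose PSA then halves satisfies section 8.1. Under the wording of section 8.2 he need not even have the fall confirmed. The rationale printed beside the 5% null concerns patients whose therapy has not changed, and radiation is a change in therapy.

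The protocol takes more care with PSA progression. Sections 7.1.2.6 and 7.1.2.11 set a start time, an eligible nadir and a confirmation rule for it.

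Two things raise the stakes. The trial is open-label and section 4.1.1 reports seven responses already seen, so unwritten rules could be settled with outcomes in view. PSA response is also the outcome of the predictive models that justify the 30 added men, so a misclassified responder enters those as well.

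**Working it through.** **1. Reproduce the plan's sample size.** Inputs from section 8.3: null 0.05, alternative 0.25, one-sided alpha 0.05, power 90%. The p-value for r responses in n is the exact upper tail

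P(X ≥ r) = 1 − Σ(i=0 to r−1) C(n,i) · 0.05^i · 0.95^(n−i).

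For n=25 and r=4: 1 − (0.2774 + 0.3650 + 0.2305 + 0.0930) = 0.0341. Power at 25% is P(X ≥ 4 | 25, 0.25) = 0.904. This is the smallest n at which the exact test first reaches 90%, so the stated 25 is right and is not in dispute.

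**2. What one man can change.** The same formula gives:

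| n | Responses needed | p at the boundary | p with one fewer |
|---|---|---|---|
| 25 | 4 | 0.034 | 0.127 |
| 28 | 4 | 0.049 | 0.163 |
| 58 | 7 | 0.025 | 0.069 |

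One man is 1/28 = 3.6 percentage points, or 1/58 = 1.7 points. He changes the conclusion only if the count sits exactly on the boundary.

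**3. How far the trial may be from the boundary.** Section 4.1.1 reports seven responses when the 38th subject had completed four cycles. Assume that all seven meet the confirmed definition and that the denominator is 38. Then 7/38 = 18.4% and p=0.0025. With two removed, 5/38 gives p=0.040. With three removed, 4/38 = 10.5% gives p=0.120. Three of the seven would have to be reclassified before significance was lost.

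**4. The denominator.** Section 8.3 speaks of evaluable patients and section 5.9 replaces only men who receive no dose, but the plan does not state the denominator. For the first stage it makes no difference to the count needed: the boundary is 4 at both 25 and 28. At the current size it does:

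| n | p for 6 responses | Responses needed |
|---|---|---|
| 53 | 0.048 | 6 |
| 54 | 0.052 | 7 |
| 58 | 0.069 | 7 |

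If 58 − 53 = 5 dosed men are set aside as not evaluable, six responses pass the test. If they are kept, six fail.

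**5. Which routes are open.** Sections 7.1.1.5.3 and 7.1.5.4.1 move a man who starts new anti-cancer therapy into survival follow-up, where the flow chart shows no PSA. That largely closes this route in practice, though not as an endpoint rule. The same sections do not clearly reach external beam radiation, which section 5.5 permits while the man stays on study. Radiation is the main route left open.

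**6. What cannot be computed.** The documents give no rate of on-study radiation, no PSA response rate after it, and no count of unconfirmed falls. Any false-positive rate would rest wholly on assumed inputs, so none is offered.

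**The case against.** - **Section 8.1 governs and is explicit.** On this view the other three places are shorthand. That is probably the intent, but section 8.2 is the sentence that specifies the test, and it defines response in its own parenthesis. The two should agree.
- **Timing is not wholly absent.** Section 7.1.5.2 says response is not officially assessed during the first four doses and refers to response at 12 weeks. This stands in part. It is a treatment rule that suggests an earliest point, and it leaves the end of the window open. The two candidate baselines are both pre-dose and at most 28 days apart, so that ambiguity alone would be a missing detail.
- **The null is not derived from the rationale.** A reader might infer that 5% assumes no change in therapy and is invalid once radiation is allowed. Section 8.3 places the two side by side without deriving one from the other, and 5% could already allow for some non-drug falls. This objection stands.
- **Irradiated men remain on the regimen.** Section 7.1.2.6 expects an immune response to take weeks or months, so a late fall after focal radiation may be a drug response. This also stands. It is why the any-time analysis belongs beside the primary one, and why a man whose fall came first should not fail only because his confirming value came after radiation.
- **Retreatment and steroid routes.** A reader might infer that falls in these settings also contaminate the endpoint. Retreatment is the tested regimen, open only after response or stability, and no section resets the baseline for it. The steroid text in section 5.5.2 is unclear rather than plainly permissive. Neither is relied on here.

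**Conclusion.** The point holds and should be fixed. As written, the plan can credit an unconfirmed fall, or a fall after permitted radiation, as a primary response in an uncontrolled test. The omission is certain on the text; its effect is unknown. It would change the conclusion only at the boundary (4 of 28, or 7 of 58). If the seven early responses all qualify among 38, the margin is three men.

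A reader might infer that the primary result is wrong, or that some of the seven responses followed radiation. Nothing in the documents supports either. This is inexpensive protection of the primary test and does not touch the sample size.

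The denominator belongs to the same point because at the current enrolment it moves the boundary from 7 to 6. Other tensions are separate and need only be reconciled: for example, section 5.5 says "Medications or vaccinations specifically prohibited in the exclusion criteria are not allowed during the ongoing trial", while section 5.5.2 says nothing is prohibited during the Monitoring Phase. The passages on recording concomitant medication (sections 5.5.1, 6.1 and 7.1.1.4.2) likewise need only be reconciled.

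**What to change.** In sections 8.1 and 8.2, with sections 3.1 and 7.1.2.12 brought into line:

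1. Define response as a fall of at least 50% from the Cycle 1 Day 1 pre-dose PSA, confirmed at least 3 weeks later. Section 5.2.2 already places assessments before dosing. Say whether values from cycles 2 to 4 can qualify, given section 7.1.5.2.
2. For the primary analysis, count a fall only if its first qualifying value precedes external beam radiation, new anti-cancer therapy and retreatment cycle 1.
3. Report two sensitivity analyses: the any-time definition with irradiated responders listed, and a version in which the confirming value must also precede radiation.
4. Count dosed men without a confirmed fall as non-responders and state the denominator. Undosed men are already replaced under section 5.9.
5. State that the rule was set after seven responses were known.

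The cost is wording and minor data checking. Section 5.5 already requires radiation dates, and neither treatment nor sample size changes. The reported rate may be slightly lower, and a delayed drug response after focal radiation would count as non-response in the primary analysis. The any-time analysis shows how many such men there are.
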